A Single Center Prospective Controlled Study of Direct Anterior Approach and Posterior Lateral Approach in the Treatment of Femoral Neck Fractures in Elderly Patients

Team leader unit: Fujian Provincial Hospital

Project leader: [name]

Responsible department: emergency surgery department

Contact number: [name]

Participants: Fujian Provincial Hospital

Study years: February 2023 - August 2024

scenario summary

project name	A single-center prospective controlled study of a direct anterior versus posterolateral approach for femoral neck fractures in very elderly patients
purpose of research	To evaluate the clinical efficacy of a direct anterior approach (DAA) versus posterolateral approach (PLA) hemiarthroplasty for femoral neck fractures in advanced elderly patients.
research design	A prospective controlled study including the patients treated for femoral neck fracture between February 2023 and 20 August 2024 were randomly ized into DAA and PLA groups according to different surgical methods for a 3-month follow-up to compare the outcomes of the two groups. Main observations include Harris hip function score (preoperative, 1 week, January, march), VAS pain score (preoperative, 1 week, January, march), secondary observations include operation time, intraoperative bleeding, blood transfusion rate, HB difference before and after surgery, CK before and after surgery, perioperative complications, postoperative lower limb length difference, postoperative discharge, postoperative ICU occupancy rate, ICU stay and total hospital stay.
Total number of cases	43 Cases
Case	① Age over 80 years old; ② confirmed unilateral femoral neck fracture by imaging examination; ③ tolerated surgery and consent to

selection	
surgery; ④ initial HA; independent walking and complete cognitive function before ⑤ injury.

	
① Bilateral femoral neck fracture; ② patients with pathological fracture; ③ with hip dysplasia and rheumatoid osteoarthritis; ④ with systemic or surgical site local infection or inflammatory reaction; ⑤ with other lower limb fractures or severe injuries to other parts of the body; ⑥ with previous history of hip surgery.

statistical method	
In this study, the statistical analysis was performed using the SPSS 27.0 statistical software.

The study period	February 2023
	August, 2024

1. research background

Femoral neck fracture is a common fracture type in the elderly, and its high disability and mortality make it a fatal killer to the life and health of the elderly. Surgery is the main treatment of femoral neck fracture in the elderly patients. Traditional femoral neck fracture in elderly patients mostly adopts the posterolateral approach (PLA) hemihip arthroplasty under spinal anesthesia, and the direct anterior approach (DAA) emerging in recent years can also be used as an option for the treatment of femoral neck fracture in elderly patients. However, due to the long learning curve of DAA, the operation is difficult, and whether this operation can be used as an effective way of femoral neck fracture in elderly patients still needs further study.

2. purpose of research

1. Primary objective: To evaluate the clinical efficacy of direct anterior approach (DAA) and posterolateral approach (PLA) hemiarthroplasty in the treatment of femoral neck fractures in elderly patients.
2. Secondary purpose: To provide some reference for the clinical treatment of femoral neck fracture in the elderly.

3. Type and principle of the study design

1. Study design

In a prospective controlled study, patients who underwent femoral neck replacement for femoral neck fracture between February 2023 and 20 August 2024 were randomly divided into DAA and PLA groups according to different surgical methods for a 3-month follow-up to compare the outcomes of the two groups.

4. Case selection

1. Inclusion criteria

① Age over 80 years old; ② confirmed unilateral femoral neck fracture by imaging examination; ③ tolerated surgery and consent to surgery; ④ initial HA; independent walking and complete cognitive function before ⑤ injury.

2. Exclusion criteria

① Bilateral femoral neck fracture; ② patients with pathological fracture; ③ with hip dysplasia and rheumatoid osteoarthritis; ④ with systemic or surgical site local infection or inflammatory reaction; ⑤ with other lower limb fractures or severe injuries to other parts of the body; ⑥ with previous history of hip surgery.

5. observation item

General information: gender, age (age), height (cm), weight (kg), comorbidity, American Association of Anesthesiologists (American Society of Anesthesiologists, ASA) classification.

Fracture related data: fracture side division, fracture Garden classification and anatomical site classification, Pauwels angle (°).

Main indicators: Harris hip function score and VAS pain score before, 1 week, 1 month and 3 months after surgery.

Laboratory indicators: hemoglobin value (hemoglobin, HB) (g / L), creatine kinase value (creatine kinase, CK) (U / L) before and after surgery, and the difference was recorded and calculated.

Surgical index: operation time (min), intraoperative blood loss (ml), and intraoperative blood transfusion rate (%).

Perioperative complications: Surgery-related complications include periprosthetic fracture, dislocation, surgical site infection and LFCN injury, while systemic complications include lower limb venous thrombosis, pulmonary infection, death, etc.

Other indicators: postoperative length difference of both lower limbs,

postoperative discharge, postoperative transfer to ICU, ICU length of stay (days), total length of stay (days), mortality rate (%).

Six, data security monitoring

The clinical study will develop a corresponding data safety monitoring plan according to the risk size. All adverse events are detailed documented, Properhandled and tracked until properly resolved or stable, Report serious adverse events and unexpected events to the Ethics committee, competent authorities, sponsor and drug regulatory department in time; A cumulative review of all adverse events was performed periodically by the principal investigator, Hold investigator meetings when necessary to assess the risks and benefits of the study; Double-blind tests may be performed for emergency unblinding when necessary, To ensure the subjects safety and rights and interests; Studies greater than the minimum risk will schedule an independent data monitor to monitor the study data, The high-risk study will establish an independent data safety monitoring board to monitor the accumulated safety data and efficacy data, To make recommendations on whether the study continues.

VII. Statistical treatment

Statistical analysis of the data was performed using the IBM SPSS Statistics 27 software. Measurement data are expressed as $x \pm s$, compared by t-test or Mann-Whitney U test according to whether the data conform to the normal distribution; count data are compared by χ^2 test or Fisher exact probability method according to the conditions. A $P < 0.05$ was considered as a statistically significant difference.

VIII. Ethics of clinical research

Clinical research will follow the provisions of the Declaration of Helsinki.

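### Does a study period ending in August 2024 cut off the 3-month assessments of patients operated on up to 20 August 2024?

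*Combined protocol and SAP*

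**What the plan says.** Section 3 (Study design) defines the population by date of operation: patients who had the replacement "between February 2023 and 20 August 2024 were randomly divided into DAA and PLA groups according to different surgical methods for a 3-month follow-up". The research design row of the summary uses the same window for "patients treated for femoral neck fracture between February 2023 and 20 August 2024". Both places attach a 3-month follow-up to those patients.

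Section 5 lists the main indicators as "Harris hip function score and VAS pain score before, 1 week, 1 month and 3 months after surgery", so the last main time point is 3 months after each patient's own operation.

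The title block gives "Study years: February 2023 - August 2024". The study period rows of the summary give the same two months. Neither place says whether the period covers intake only or the whole study, and the text gives no date for the last visit, database lock or study end.

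**The concern.** Read literally, three statements do not fit together: operations up to 20 August 2024, a 3-month assessment for each patient, and a study that ends in August 2024. If August 2024 were the end of data collection, patients operated on in the last three months or so of the window would have no 3-month Harris or VAS score within the study. The very last patients would miss the 1-month score as well.

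In a trial of 43, losing several patients at a main time point would matter. Section VII (Statistical treatment) has no rule for incomplete follow-up, so the analyst would have no guidance on whether to drop such patients or use an earlier visit. No direction of bias could be derived, because both groups come from the same window.

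**Working it through.** **Inputs from the document**
- Last permitted operation: 20 August 2024 (summary and section 3).
- Last main time point: 3 months after surgery (section 5).
- Stated end: August 2024 with no day (title block and summary). Both 20 and 31 August are tried.
- Total patients: 43 (summary).
- Assumed: a start on 1 February 2023, since no day is given.

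**Calendar check for a patient operated on 20 August 2024**
- 1 week: 27 August 2024, inside the period if it ends on 31 August.
- 1 month: 20 September 2024, outside.
- 3 months: 20 November 2024, outside (18 November if 3 months is taken as 90 days).
- 31 August to 20 November is 81 days; 20 August to 20 November is 92 days.

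Working backwards, the last operation whose 3-month visit fits is 31 May 2024 for a 31 August end, or 20 May 2024 for a 20 August end. The date arithmetic behind the concern is right.

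**How many patients would be affected if August 2024 were a cut-off**

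The window from 1 February 2023 to 20 August 2024 is T = 566 days. The late share is f = d/T, that is 81/566 = 0.143 or 92/566 = 0.163. The document gives no accrual pattern, so each count below rests on an assumed one.

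| Assumed accrual | Formula | d = 81 | d = 92 |
|---|---|---|---|
| Everyone treated before the late stretch | none late | 0 | 0 |
| Falling linearly to zero | 43 × f² | 0.9 | 1.1 |
| Even | 43 × f | 6.2 | 7.0 |
| Rising linearly from zero | 43 × (1 − (1 − f)²) | 11.4 | 12.8 |

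The range of 0 to about 13 reflects only the assumed shapes. The document supports no narrower statement than: number unknown, possibly zero.

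**Does the plan make August 2024 a cut-off?**
- The stated period and the treatment window both run from February 2023 to August 2024. If all these statements describe intake, no two dates disagree, and follow-up runs on after the window closes.
- Follow-up is set per patient: 3 months for those included, with scores timed from each operation. That is the specific instruction; the study period is a general heading.
- Nothing in the text sets a data cut-off or database lock, or tells the team to leave out patients with incomplete follow-up. Losing data would need a step that the plan does not contain.

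**The case for a change.** The strongest case for acting is that the intake-only reading is an inference. Nothing in the text labels the period that way, and if it does mean intake, the end of follow-up is stated nowhere. The other way to reconcile the dates, a window that already includes follow-up, is hard to hold because section 3 ties the window to patients who had the operation within it. On either reading a line of text would help, and it would cost almost nothing.

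Most of this stands as description: the end of follow-up is not stated, and a label would make the document clearer. It does not establish a flaw in design or analysis. The claim of a contradiction depends on taking the period to mean the whole study, while the matching endpoints point to intake. The claimed harm also needs someone to override the explicit 3-month schedule with an administrative heading. The absence of a missing-visit rule in section VII is a separate matter and is not caused by these dates.

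**Conclusion.** The concern does not call for a change to the plan. The arithmetic is correct: the last 3-month assessment falls on about 20 November 2024, 81 to 92 days after the stated end. The consequence does not follow. Carried out as written, the plan yields Harris and VAS scores at 3 months for every patient who can be assessed, including those operated on in August 2024.

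This rests on two points: the stated period is read as the intake window, whose endpoints it shares, and no cut-off in August 2024 is set in the text. If the team had in fact closed data collection in August 2024, the 3-month scores of late patients would be lost, but the document does not say so and the number cannot be derived from it. What remains is an unlabelled administrative date. Labelling it would change no patient, visit, test or conclusion.

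### The protocol does not say clearly whether the approach was assigned by chance, and Section VII makes no use of the preoperative scores or baseline covariates it collects

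*Combined protocol and SAP*

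**What the plan says.** **Allocation.** Section 3 (Study design) states that patients "were randomly divided into DAA and PLA groups according to different surgical methods for a 3-month follow-up". The research design row of the scenario summary has the same clause: "were randomly ized into DAA and PLA groups according to different surgical methods for a 3-month follow-up". The title reads "A Single Center Prospective Controlled Study of Direct Anterior Approach and Posterior Lateral Approach" and does not mention randomisation. Section 3 applies the division to "patients who underwent femoral neck replacement for femoral neck fracture between February 2023 and 20 August 2024". The supplied text gives no method, timing, ratio or concealment of assignment. Four passages were removed before review, so this describes the supplied text and not necessarily the whole protocol.

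**Data collected.** Section 5 lists as main indicators "Harris hip function score and VAS pain score before, 1 week, 1 month and 3 months after surgery". It also lists baseline characteristics, beginning "General information: gender, age (age), height (cm), weight (kg), comorbidity, American Association of Anesthesiologists", together with the fracture classifications.

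**Analysis.** Under Section VII, measurement data are "compared by t-test or Mann-Whitney U test according to whether the data conform to the normal distribution", and count data by chi-square or Fisher exact test, at a 0.05 level. No covariate, including the preoperative score, has a role in any comparison.

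**The concern.** One clause carries two ideas. The word *randomly* says that chance decided the group. The words about surgical methods can simply name the two arms, or can say that the operation performed decided the group. The same p-value supports different conclusions in the two cases.

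- **Chance assignment:** baseline differences are chance, and each unadjusted test keeps its 5% error rate. The plan only forgoes whatever precision the preoperative score offers.
- **Grouping by approach used:** a Harris or VAS difference at 1 week, 1 month or 3 months may partly reflect who was selected for DAA. Section VII has nothing to account for that, and the report would still carry the word *randomly*.

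Selection would be plausible if the choice was free, because Section 1 describes DAA as difficult and slow to learn, and PLA as the usual approach. That is a reason to ask the question; it does not show that selection took place.

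**Working it through.** **1. What the plan's own figures allow.** The only design figure is the total of 43 patients in the scenario summary. It comes without an effect size, SD, power or group split, so there is no calculation to reproduce. The steps below take 43 complete patients, a 21/22 split and two-sided 5% tests. The split, the completeness and the two-sidedness are assumptions.

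**2. Text check.** For chance assignment: *randomly* appears in both places, and DAA and PLA are themselves surgical methods, so the rest of the clause may only label the arms. For grouping by approach used: the literal sense of the clause. Neutral: the title (a controlled study may be randomised) and the past tense for the operated patients (Section VII also uses the past tense for the planned analysis, so tense says nothing about timing). The wording leaves both readings open.

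**3. Reading A, chance assignment: what is given up without the preoperative score.** With k covariates in N patients, the variance of the approach effect relative to the unadjusted comparison is (1 − r²) × [1 + k/(N − k − 3)], where r is the (multiple) correlation of the covariates with outcome.

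For k = 1 and N = 43 the factor is (1 − r²) × (1 + 1/39):

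| r | variance ratio | change |
|---|---|---|
| 0 | 1.026 | +2.6% |
| 0.2 | 0.985 | −1.5% |
| 0.3 | 0.933 | −6.7% |
| 0.5 | 0.769 | −23% |

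Break-even is at 1 − r² = 39/40, so r = √0.025 = 0.158. The documents do not give r.

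**4. Reading B, grouping by approach used: what case mix does to an unadjusted t-test.** Suppose approach has no effect, and the groups differ by m SD on one factor that correlates r with outcome. The bias is m × r SD. The standard error is √(1/21 + 1/22) = 0.305 SD, so the noncentrality is m × r / 0.305 on 41 df. The values of m and r are assumed, because the documents contain no case-mix data.

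| m | r | bias (SD) | noncentrality | false-positive rate per test |
|---|---|---|---|---|
| 0.3 | 0.3 | 0.09 | 0.295 | 6.0% |
| 0.3 | 0.5 | 0.15 | 0.492 | 7.7% |
| 0.5 | 0.3 | 0.15 | 0.492 | 7.7% |
| 0.8 | 0.3 | 0.24 | 0.787 | 12.0% |
| 0.5 | 0.5 | 0.25 | 0.819 | 12.6% |
| 0.8 | 0.5 | 0.40 | 1.311 | 24.9% |

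With an 11/32 split the same range runs from 5.7% to 20.1%.

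**5. What adjustment does under reading B.** In simulation (100,000 trials per case, 21/22, no true effect), a regression that includes the responsible factor has an error rate of 5.0% to 5.1%. If the factor is unmeasured, the rate stays at 12.0% (m = 0.5, r = 0.5) and 23.4% (m = 0.8, r = 0.5). Adjustment therefore deals only with factors that are in the model.

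**6. Cost in degrees of freedom.** Intercept, approach and preoperative score are 3 parameters, leaving 43 − 3 = 40 df. With age and ASA class as one term each there are 5 parameters and 38 df. If all three covariates were unrelated to outcome, the variance would rise by 3/37 = 8.1%.

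**The case against.** The strongest reply is that the text leans towards randomisation. The word *randomly* appears in both places, the document reads as a translation, and the rest of the clause may do no more than name the arms. If so, Section VII is valid as written, and all that is missing is a reporting sentence, which could have been in the removed passages. This stands to a large extent: it rules out any claim that bias has been shown, and it lowers the severity.

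The size of the harm is also assumed throughout. With correlations of 0.1 to 0.2 and the same imbalances, the false-positive rate is only 5.1% to 8.1%. The 24.9% needs a large imbalance, a moderate correlation and non-random allocation all at once. This stands too.

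Finally, regression under random assignment can be called a preference, since the t-test is then valid and the correlation is unknown. It is true that no error needs correcting in that case. But the cost is bounded at 2.6% of variance, the gain begins at a correlation of about 0.16, and the scores are already collected. The change is worth making whichever reading is right.

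A reader might infer that the study was not randomised. The documents do not support that: the clause is ambiguous, and neither the title nor the tense decides it. Nor do they support the inference that Section VII is invalid in itself, because that depends on the second reading.

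**Conclusion.** The point holds as an ambiguity joined to an analysis that leaves collected information unused. The plan should be changed on both counts, as a should-fix item.

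- **Certain from the supplied text:** the clause admits two readings, nothing supplied resolves it, and Section VII adjusts for nothing.
- **Conditional on chance assignment:** each test keeps its 5% error rate, and the loss is one of precision if the preoperative score correlates above about 0.16 with outcome.
- **Conditional on grouping by approach used:** the false-positive rate per test is roughly 6% to 25% over the assumed range. The low end is negligible and the high end is not.

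The rates are for a single test and say nothing about multiplicity over time points. They rest on 43 complete patients, a 21/22 split and assumed imbalances and correlations. They should not be read as an estimate of bias in this study.

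**What to change.** **1. Section VII, under either reading.** Compare Harris and VAS at 1 week, 1 month and 3 months by linear regression on approach and the preoperative value of the same score. If residuals are clearly non-normal, check with the same model on ranks or with a bootstrap interval, in place of switching to Mann-Whitney.

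**2. Section 3 and the scenario summary: state what was actually done.**

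- *If a chance process set the approach before surgery:* delete the words about surgical methods. Give the method, timing, ratio and concealment of assignment, and analyse patients in the group assigned. If allocation was not concealed, report that as a limitation; it does not by itself make the study non-randomised.
- *If it was anything else (choice by surgeon or patient, schedule, alternation, record number):* delete *randomly* and report a non-randomised comparison. Add age and ASA class to the regression as one term each, fixed before outcomes are compared. Present the unadjusted secondary outcomes (the summary's "secondary observations include operation time, intraoperative bleeding, blood transfusion rate" and the rest of that list) as descriptive, and state that unmeasured confounding remains.

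**Cost.** Wording in two places and six regressions (two scores, three time points) on variables already collected, with no extra patients or visits. The regression costs 1 df (at most 2.6% more variance) under chance assignment, or 3 df (at most 8.1%) otherwise, assuming 43 complete patients. Deaths or losses reduce this further: the five-parameter model has 34 df with 39 patients and 29 with 34. Under the second branch the conclusion is also weaker, and adjustment cannot remove confounding by factors that were not recorded.

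### If assignment is random, nothing hides the next allocation from a team applying entry criteria without cut-offs, so selection bias is possible and the Section VII tests cannot remove it

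*Combined protocol and SAP*

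**What the plan says.** Assignment is described in one sentence, given twice. The scenario summary has patients "randomly ized into DAA and PLA groups according to different surgical methods". Section 3 (Study design) uses nearly the same phrase, "randomly divided into DAA and PLA groups according to different surgical methods", and defines the population in the past tense, as "patients who underwent femoral neck replacement for femoral neck fracture between February 2023 and 20 August 2024". Neither place gives a method of generating the sequence, a ratio, blocks or strata, a holder of the list, or the point at which assignment happens relative to the eligibility decision and the operation.

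Section 4 sets entry partly by judgement. Patients must have "tolerated surgery and consent to surgery" and "independent walking and complete cognitive function before" injury, and are excluded "with systemic or surgical site local infection or inflammatory reaction". No instrument or threshold is attached to any of these. The study runs at one hospital under one responsible department, and the background section describes the anterior approach (DAA) as hard to perform and slow to learn.

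Section 5 records, under "General information: gender, age (age), height (cm), weight (kg), comorbidity", several prognostic factors, and ASA class is in the same list. Section VII uses none of them: it names only t, Mann-Whitney, chi-squared and Fisher tests at P < 0.05. The total is 43 cases. The only text near blinding is a general sentence on emergency unblinding in Section Six, which does not concern concealment of assignment.

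**The concern.** Random assignment protects a comparison only if whoever decides on entry cannot foresee the next arm. Here the operation is visible to the department, entry involves discretion, and one of the two operations is acknowledged to be harder. Someone who knows that the next slot is DAA could judge a borderline patient ineligible, or judge a PLA candidate more leniently. The arms would then differ in prognosis before surgery.

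Patients turned away never enter the data set, so no test in Section VII can recover the comparison. The bias could run in either direction and would reach any outcome that depends on prognosis, including the two main ones, the Harris and VAS scores. Without a log of screened patients, nobody could later show that it had not happened.

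**Working it through.** **Plan's own figure.** The 43 cases cannot be reproduced, because no effect size, SD, power, dropout or ratio is given. I take arms of 21 and 22 and a two-sided 5% level (Section VII does not state the sidedness).

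**1. Possible selection bias.** Assumed, since the documents give no values: frail share of candidates p = 0.40; frailty effect D = 0.5 or 1 SD; fraction f of frail patients screened out before DAA slots = 0.5, 0.75 or 1; no screening before PLA slots; no true difference.

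Frail share in DAA = p(1−f) / [p(1−f) + 1 − p]:
- f = 0.5: 0.20/0.80 = 0.25
- f = 0.75: 0.10/0.70 = 0.143
- f = 1: 0/0.60 = 0

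PLA stays at 0.40. Bias = (0.40 − DAA share) × D. Standard error = √(1/21 + 1/22) = 0.305 SD. The error rate is the rejection rate of a t-test on 41 degrees of freedom, shifted by bias/0.305.

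| f | Difference in frail share | Bias, D = 0.5 | Error rate | Bias, D = 1 | Error rate |
|---|---|---|---|---|---|
| 0.5 | 0.15 | 0.075 SD | 5.7% | 0.15 SD | 7.7% |
| 0.75 | 0.257 | 0.129 SD | 7.0% | 0.257 SD | 13.1% |
| 1 | 0.40 | 0.20 SD | 9.8% | 0.40 SD | 24.9% |

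These rates treat 1 SD as the total SD. If it is the SD within frailty groups, the D = 1 rates fall to 7.3%, 11.8% and 22.2%.

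**2. Chance imbalance, a separate matter.** Under simple randomisation of 43, P(27:16 or worse) = 2 × P(Bin(43, 0.5) ≤ 16) = 12.6%. The cost is small: √[(1/27 + 1/16)/(1/21 + 1/22)] = 1.034, a 3.4% larger standard error. A difference of 20 points or more in the share with ASA III or higher arises in 16% to 21% of trials (assumed prevalence 30% to 70%). This does not inflate false positives: with simple randomisation, 50% prevalence and a 1 SD effect, the unadjusted t-test rejects in about 5.1% of simulated null trials.

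**3. What leaving out ASA costs.** Assume 50% prevalence, within-class SD of 1, a true difference of 0.8 SD and arms of 21 and 22.
- Unadjusted SD = √(1 + 0.25D²): 1.031 at D = 0.5 and 1.118 at D = 1. The signal is 0.8/(1.031 × 0.305) = 2.54 and 0.8/(1.118 × 0.305) = 2.35. Power is 70% and 63%.
- Adjusted, on 40 degrees of freedom: (0.8/0.305) × √(1 − 1/42) = 2.59. Power is 72% in both cases.

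If arm sizes are left to chance, power is one or two points lower. Overall the gain is from about 70% to 72% at D = 0.5, and from about 61–63% to 69–72% at D = 1.

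**4. Would stated blocks help?** With two strata and known block sizes of 2 and 4 (equally likely), someone tracking past assignments guesses 71.5% of the 43 correctly in simulation, and knows about 10% with certainty. Simple randomisation allows 50%.

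**The case against.** The strongest objection is that the point depends on an unsettled reading. The sentence concerns patients who had already been operated on and divides them by surgical method. If grouping followed the operation received, concealment is not the issue and confounding by indication takes its place. That stands, and is why the wording comes first.

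The magnitudes also rest wholly on assumed values. Screening out half to all frail patients before every DAA slot needs good foreknowledge, used consistently in one direction; guessing alone would do less. Requiring independent walking and intact cognition before injury already narrows the range of frailty, although age over 80, comorbidity and ASA class still vary. At a 0.5 SD effect with half screened out, the inflation is slight. No section says who recruits or how operations are scheduled. All of this stands and limits the size of the point, but it does not supply the missing concealment.

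Three stronger inferences are not supported:
- A reader might infer that steering took place. The documents show only that nothing prevents it.
- A reader might infer that missing stratified blocks let patients be steered. They do not: simple randomisation is the hardest scheme to guess, and the opening comes from missing concealment.
- A reader might infer that chance imbalance in ASA class adds to the false-positive rate. It does not; a valid test already allows for it, and the loss is in precision.

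**Conclusion.** The gap stands, provided that assignment is meant to be random. The plan then offers nothing beyond the word itself to keep the next assignment from a single-centre team using entry criteria without cut-offs, and its analysis cannot repair any resulting selection. The possible bias is about 0.08 to 0.40 SD, with a true error rate of about 6% to 25% against a nominal 5% (slightly lower at the top if the SD is within frailty groups). Both ranges depend on the assumed 40% frail share, the 0.5 to 1 SD effect and the screening fractions.

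The omission of ASA from the analysis is a smaller and distinct matter: a few points of power, up to about nine if ASA shifts the outcome by a full SD. The conclusion on concealment is firm under the random reading; its size is not.

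**What to change.** **Section 3.** First state whether assignment is random or follows the operation received. If random, state that a computer-generated 1:1 sequence is prepared and held outside the operating department, in sequentially numbered, opaque, sealed envelopes, each opened only after consent and a signed eligibility check. Keep a log of every screened patient with the reason for any exclusion. If blocks are used, vary their sizes and keep the sizes out of the protocol and from recruiters.

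**Section VII.** Compare the Harris and VAS scores with a linear model that includes ASA class (I–II v III or higher, already recorded), and keep the unadjusted tests as supporting analyses.

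**Cost.** No extra patients. There is a short administrative step before each operation, one degree of freedom for ASA class, and a regression model in place of the t-test, which Section VII does not now provide for.

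### No primary score, visit or success rule: six postoperative Harris and VAS comparisons, each at P < 0.05, carry about an 11 to 26% chance of a false difference (assumed correlation 0.9 to 0), not 5%

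*Combined protocol and SAP*

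**What the plan says.** Section 2 (Purpose of research) frames the aim broadly: "Primary objective: To evaluate the clinical efficacy of direct anterior approach (DAA) and posterolateral approach (PLA) hemiarthroplasty". It ties that aim to no score, visit or result that would count as success. Section 3 (Study design) plans "for a 3-month follow-up to compare the outcomes of the two groups", which fixes the length of follow-up but not a primary visit.

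Section 5 (Observation item) lists "Main indicators: Harris hip function score and VAS pain score before, 1 week, 1 month and 3 months after surgery". The synopsis has the same pair: "Main observations include Harris hip function score (preoperative, 1 week, January, march), VAS pain score (preoperative, 1 week, January, march". Its month names evidently stand for the 1-month and 3-month visits in section 5. The synopsis places operation time, bleeding, transfusion, complications, length of stay and other items in a separate secondary tier. Within the main tier, neither score and none of the visits is ranked above the others.

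Under section VII (Statistical treatment), measurement data are "compared by t-test or Mann-Whitney U test according to whether the data conform to the normal distribution", and P below 0.05 "was considered as a statistically significant difference". The section gives no repeated-measures model, order of testing or adjustment for several comparisons. Preoperative scores appear among the main indicators and are not labelled as baseline values.

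**The concern.** A threshold of 0.05 controls the error of one comparison. The primary objective calls for one conclusion about efficacy, and the plan does not say how six postoperative results lead to it. If VAS differed at 1 week while neither score differed at 3 months, one reader could report that the anterior approach is more effective and another that it is not. The text would support either.

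With no rule fixed in advance, the choice of which result counts can be made after the data are seen. The trial has 43 patients and no stated effect size or power. Of the six results, the one that happens to cross 0.05 could become the headline, and the plan would give no ground for objecting.

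**Working it through.** **Inputs from the documents**
- Main scores: 2 (section 5 and synopsis).
- Postoperative visits: 3 (1 week, 1 month, 3 months).
- Threshold: 0.05 per comparison (section VII).
- Total patients: 43 (synopsis).

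**Assumptions**
- Two-sided tests; the documents do not state sidedness.
- A 21/22 split with complete data; allocation and losses are not stated.
- No true difference between approaches, and groups comparable apart from chance.
- Correlations between the six comparisons; none is given, so a range is shown.
- Any one significant result is read as a difference.

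**The plan's own figures.** No overall error rate is stated, so there is none to reproduce. The 43 cannot be re-derived because effect size, SD, power, allocation ratio and dropout are not given. The point does not depend on how 43 was chosen.

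**Step 1: count.** 2 scores × 3 visits = 6 comparisons. Testing the two preoperative scores as well would make 8.

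**Step 2: uncorrelated comparisons.** 1 − 0.95^6 = 1 − 0.7351 = 0.265.

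**Step 3: common correlation r.** The chance of at least one significant result is

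1 − ∫ φ(u) [Φ((1.96 − √r·u)/√(1−r)) − Φ((−1.96 − √r·u)/√(1−r))]^6 du.

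This was checked by simulating six pooled t-tests with 21 and 22 patients (40,000 replicates).

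| Assumed r | Integration | Simulated t-tests |
|---|---|---|
| 0 | 26.5% | 26.4% |
| 0.3 | 24.1% | 23.9% |
| 0.5 | 20.7% | 21.3% |
| 0.7 | 16.4% | 16.5% |
| 0.8 | 13.9% | 13.9% |
| 0.9 | 10.8% | 11.1% |

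**Step 4: different correlations within and between scores (simulated).** With 0.7 within a score and 0.4 between scores, 19.7%. With 0.8 and 0.5, 17.4%.

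**Step 5: smaller and larger families.** Two scores at one visit, unadjusted: 1 − 0.95^2 = 9.75% at r = 0, falling to about 7% at r = 0.9. Eight comparisons: 1 − 0.95^8 = 33.7% at r = 0 and 11.9% at r = 0.9.

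**Step 6: what control would cost.** The detectable difference d, in SD units, solves: power of a two-sided t-test with noncentrality d·√(n₁n₂/(n₁+n₂)) = 0.80. The levels are 0.05 for one test, 0.05/2 = 0.025 for the first Holm step across two, and 0.05/6 = 0.0083 for the first Holm step across six.

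| Patients per group | One test | Holm, two | Holm, six |
|---|---|---|---|
| 21/22 | 0.875 | 0.971 | 1.109 |
| 19/20 | 0.922 | 1.023 | 1.170 |
| 14/29 | 0.934 | 1.035 | 1.183 |

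At 0.05/6 per test, the simulated chance of any false result is 4.8% at r = 0 and 2.2% at r = 0.9.

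**The case against.** The percentages need a rule that the plan never states. They apply only if one significant result of the six is enough. If all six had to be significant, simulation gives a false-positive chance of 1.5% or less for r up to 0.9. Nor does the plan claim a 5% overall rate; its 0.05 is plainly per comparison. Zero correlation is unrealistic for the same patients' scores over three months, so 26% is a bound, and a correlation of 0.95 would bring the figure down to 8.9%. The synopsis does separate main from secondary observations. Finally, the aims are modest (to evaluate, and to offer a reference for practice), so calling the comparisons exploratory would largely settle the matter.

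Much of this stands as qualification. The figures are conditional on the any-one reading, the more structured scenarios give 17 to 20%, and the main/secondary split does narrow the choice to two scores. The label on the preoperative scores is a minor point and does not enter the six-test calculation.

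None of it closes the gap. The plan states neither an all-six rule nor an exploratory purpose, and it does call its aim the primary objective. Section VII lets any single comparison below 0.05 be declared a significant difference, so the any-one reading is open to whoever writes the report. Even at a correlation of 0.95 the error exceeds 5%.

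**Conclusion.** The concern holds. The primary objective has no single score, visit, order of testing or success rule, and section VII applied as written does not hold the false-positive rate for an efficacy conclusion at 5%. If any one of the six results may count, the rate is about two to five times the nominal level. Where it falls in that range depends on correlations that the documents do not supply.

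The figures describe chance error only. The text says patients were randomly divided but also that this followed the surgical method used. If allocation in fact followed the choice of surgery, confounding would come on top of these figures.

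This should be settled before outcomes are analysed, because it cannot be repaired once the results are known.

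**What to change.** In section VII, name one primary score and one primary visit. The choice belongs to the investigator. Example wording: *The primary outcome is the Harris score at 3 months (end of follow-up), tested at two-sided 0.05; VAS at 3 months is tested only if Harris is significant.*

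Alternatives:
- If both scores stay primary, apply Holm across the two tests at one visit. Requiring both to be significant at 0.05 also needs no adjustment, but it costs power.
- If all visits must stay confirmatory, apply Holm across all six tests.

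Report visits outside the chosen tests as secondary, as differences with 95% confidence intervals and not as grounds for an efficacy claim. Label the preoperative scores as baseline values. If outcomes have already been analysed, say so and call the six comparisons exploratory.

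Only SAP wording changes. Under the one-visit options the other visits lose confirmatory status. With 21/22 patients and complete data, the detectable difference at 80% power is 0.88 SD for one primary test. It rises to 0.97 SD for the first-tested score under Holm across two and to 1.11 SD under Holm across six. Losses to 39 assessed patients (19/20) or a 14/29 split would raise each by about 0.05 to 0.07 SD.
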